### 9.3.2. Interim Analysis

A formal interim analysis will be conducted during the study. Additionally, two review teams will monitor data on an ongoing basis for routine pharmacovigilance and decision making regarding the subsequent clinical development of GSK2982772 for RA.

In line with routine pharmacovigilance, an internal GSK Safety Review Team (SRT) which will include members of the GSK2982772 project team, will review blinded safety

data, including clinical laboratory parameters and adverse events, at appropriate intervals during the period of study conduct.

Once an appropriate number of subjects have completed Day 43 (Week 6) the DAS28-CRP data will be reviewed in an unblinded manner and on an ongoing basis by the Data Review Committee, consisting of the GSK Project Physician Lead (PPL), the study statistician, the study pharmacokineticist, the PRR DPU Head, EDL and SRT Leader or designees on an ongoing basis. A physician external to the GSK2982772 project team may also be involved in the data review. Additional inflammatory biomarkers, clinical and mechanistic endpoints (e.g. target engagement) may be reviewed if available. No other member of the GSK core study team will be unblinded to this data. The primary purpose of these informal reviews will be to monitor DAS28-CRP for futility. On review of DAS28-CRP data, the review group may recommend an interim analysis of key clinical and mechanistic data is first conducted prior to any decision to terminate the study for futility. A data review charter will identify the specific GSK individuals involved, outline in detail the activities of this review and how the integrity of the study will be maintained.

A formal interim analysis will be conducted during the study. The timing of this analysis will either be on the recommendation of the data review group to assess futility based on 6 weeks of treatment, or when an appropriate number have completed 12 weeks of treatment, whichever is earliest. The purpose of the Interim Analysis would be to assess whether to stop the study for futility. This interim analysis may also facilitate decision making regarding the subsequent clinical development of GSK2982772 for RA.

## **9.4. Key Elements of Analysis Plan**

### **9.4.1. Primary Analyses**

All safety evaluations will be based on the Safety population. Clinical interpretation will be based on the review and displays of adverse events, clinical laboratory values, vital sign measurements and 12-lead ECG monitoring.

### **9.4.2. Secondary Analyses**

The relationship between each of the mechanistic endpoints and also with the clinical endpoints will be graphically presented and analysed using an appropriate statistical model identifying any trends. The model will determine whether the mechanistic effect significantly explains or predicts the effect on the other mechanistic or clinical endpoints (e.g., DAS28-CRP score). This may be conducted through comparing statistical models incorporating different explanatory terms (i.e. mechanistic endpoints) with the 'null' model (no mechanistic endpoints); or if deemed appropriate, multivariate statistical methods may also be applied to determine the relationship between the key endpoints. The consistency in the changes over time between the endpoints will also be assessed.

Each endpoint will be considered individually and at the treatment level, where comparisons between treatment groups would be made on any changes observed, if deemed appropriate. This could include change from baseline in DAS28-CRP, which will be statistically analysed using a MMRM analysis comparing GSK2982772 with placebo

at each time point. Additionally, this could include, the proportion of subjects achieving ACR20/50/70 and DAS28-CRP response, which will be statistically analysed using a Generalised Estimating Equation (GEE) model comparing GSK2982772 with placebo at each timepoint. Similar analyses will be conducted for other secondary endpoints if deemed appropriate.

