##### **7.4.2.2. American College of Rheumatology Criteria (ACR) Assessments**

The ACR Criteria is a standard criteria to measure the effectiveness of treatments from placebo. The ACR’s definition for calculating improvement in RA (ACR20) is calculated as a 20% improvement in tender and swollen joint counts and 20% improvement in 3 of the 5 remaining ACR-core set measures: patient and physician global assessments, pain, disability, and an acute-phase reactant. Similarly, ACR50 and 70 are calculated with the respective percent improvement.

The specific components of the ACR Assessments that will be used in this study are:

- Tender/Painful Joint count (28)
- Swollen Joint Count (28)
- Patient Assessment of Joint Pain
- PtGA
- PGA
- CRP
- HAQ-DI

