### **7.4.2.4. Measurement of Serum CRP**

Blood samples will be collected in order to measure serum CRP concentrations. The CRP is a component of the DAS28, ACR, and Vectra DA clinical scores.

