## 9. STATISTICAL CONSIDERATIONS AND DATA ANALYSES

### 9.1. Hypotheses

The primary objective of the study is to investigate the safety and tolerability of GSK2982772 following 12 weeks of treatment. No formal statistical hypotheses will be conducted to assess this objective.

If appropriate, comparisons between the GSK2982772 and the placebo arm will be made to investigate the secondary pharmacodynamic, mechanistic and efficacy objectives.

Trends over time will be investigated for both treatment arms along with associations between each of the pharmacodynamic, mechanistic and efficacy parameters.

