### Synopsis and Section 3 Objectives and Endpoints

Objectives	Endpoints
Primary	

 
To investigate the safety and tolerability of 60 mg <del>twice</del> three times daily doses of GSK2982772 in subjects with moderate to severe Rheumatoid Arthritis.
 
	
 
Adverse events.
 
Clinical laboratory values (clinical chemistry, haematology and urinalysis).
 
Vital sign measurements (blood pressure, heart rate, respiratory rate, and body temperature).
 
12-Lead ECG monitoring.
 

Secondary	

 
To investigate the plasma concentrations of GSK2982772 following 60 mg <del>twice</del> three times daily doses of GSK2982772 in subjects with moderate to severe Rheumatoid Arthritis.
 
	
 
Pre-dose concentrations of GSK2982772 on Days 8 and 43 (Week 6).
 
Post-dose concentrations of GSK2982772 on Days 1, 8, and 43 (Week 6) at 1, 2, 4 and 6 hours.
 
Trough concentrations on Day 85 (Week 12).
 

 
To investigate the effect of 60 mg <del>twice</del> three times daily doses of GSK2982772 on inflammatory biomarkers in blood subjects with moderate to severe Rheumatoid Arthritis.
 
	
 
Change from baseline in blood inflammatory markers (e.g., may include but not limited to CRP, IL6, MMP-1, MMP-3, MMP-13, TIMP-1, MCP-1, MIF, MRP8/14 and other markers encompassed by Vectra DA).
 

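### If CRP is used as an explanatory marker, as Section 9.1 implies, its association with DAS28-CRP is partly arithmetic and could be declared explanatory

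*Protocol*

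**What the plan says.** Four places in the protocol bear on this.

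- **Section 9.4.2 (Secondary Analyses)** states the aim: "The model will determine whether the mechanistic effect significantly explains or predicts the effect on the other mechanistic or clinical endpoints". DAS28-CRP is the only outcome named as an example. One permitted route is to compare a model that contains the marker with a null model that does not; multivariate methods are another.
- **Section 9.1 (Hypotheses)** sets the scope: "associations between each of the pharmacodynamic, mechanistic and efficacy parameters".
- **Section 3 (Objectives and Endpoints, including the version in Amendment 3)** has a secondary endpoint that opens "Change from baseline in blood inflammatory markers (e.g., may include but not limited to CRP, IL6". CRP is the first marker on that list.
- **Section 7.4.2.4** states: "The CRP is a component of the DAS28, ACR, and Vectra DA clinical scores". Section 7.4.2.1 also lists CRP among the four DAS28 components, with tender joints, swollen joints and patient global.

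Nothing in the text at hand excludes CRP as an explanatory variable or provides an outcome without CRP for that case.

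**The concern.** The question in 9.4.2 is whether an effect on a marker explains an effect on disease activity. Comparing models with and without the marker tests something else, namely whether the association between marker and score is zero. For most markers the difference is harmless. For CRP against DAS28-CRP it is not: CRP enters the score, so the association is not zero even when CRP is unrelated to joint counts and patient global. A significant result cannot separate explanation from arithmetic.

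What is at stake is interpretation. The study rationale says these endpoints should broaden understanding of the mechanism and of the potential for efficacy. A finding that CRP explains DAS28-CRP could be reported as mechanistic support when part of it is the marker predicting itself.

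**Working it through.** **The plan's own figure.** The protocol gives no figure for the association models. Its nearest figure is the precision of the change in DAS28-CRP in Section 9.2.1, with SD = 1. The half-width of the 95% CI is 1.96 × SD / √n.

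- n = 16: 1.96 × 1 / 4 = 0.490
- n = 8: 1.96 × 1 / 2.828 = 0.693

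Both match the protocol's values, so SD = 1 is used below.

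**Inputs**

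- From the protocol: SD of change 1; 2:1 allocation; about 24 subjects on the TID regimen (16 and 8); totals of 36 and 42 from Table 4.
- Assumed: two-sided 5% test, since 9.4.2 says only that the effect is to be significant; adjustment for arm; joint counts and patient global independent of CRP.
- Assumed: CRP's share *s* of the variance of the change in DAS28-CRP is 5% to 30%. The protocol gives neither the DAS28 weights nor the variability of CRP. As a rough guide to the range, an assumed weight of 0.36 on log CRP, an SD of log change of 0.6 to 1.2 and assumed spreads for the other components give shares of about 5% to 27%.

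**Model.** Change = C + R, where C is the CRP term with variance *s* and R is the rest with variance 1 − *s*, independent of C. The correlation of CRP with the score is then √s, not zero: 0.22 at *s* = 0.05 and 0.55 at *s* = 0.30.

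**Result.** Rejection rate of the test of the CRP term against the model without it (5,000 runs per cell):

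| CRP share | N = 24 | N = 36 | N = 42 |
|---|---|---|---|
| 5% | 18% | 26% | 29% |
| 10% | 32% | 47% | 53% |
| 15% | 46% | 65% | 73% |
| 20% | 59% | 78% | 86% |
| 30% | 80% | 95% | 97% |

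Hand check at N = 24 and *s* = 0.10: the expected t is about √(22 × 0.10/0.90) = 1.56. The critical value on 21 degrees of freedom is 2.08. The chance of exceeding it is roughly P(Z > 0.52) = 0.30, against 0.32 simulated.

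**A second set of assumptions.** A CRP weight of 0.30 to 0.36 and an SD of log change of 0.5 to 1.0 give shares from 0.30² × 0.5² = 2% to 0.36² × 1.0² = 13%. At 16 and 8 subjects, with a treatment term, rejection is 10% to 42%. This agrees with the table where the ranges overlap.

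**With the CRP term removed.** When R alone is the outcome, rejection is 4.4% to 5.5% over all the shares and sample sizes in the table.

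**ACR response.** Section 7.4.2.2 requires improvement in both joint counts and "20% improvement in 3 of the 5 remaining ACR-core set measures"; CRP is one of those five. Simulated with CRP independent of the other six components, improvement probabilities of 0.4 to 0.6 and correlations of 0 to 0.7 among the others (4,000 runs per cell, logistic likelihood-ratio test):

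- N = 24: 6.4% to 10.5%, against 5.6% to 7.7% with CRP permuted.
- N = 42: 6.0% to 11.2%, against 5.4% to 6.7% with CRP permuted.

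The largest excess in any cell is 11.2 − 6.5 = 4.7 points. It is close to zero when the other components are strongly correlated.

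**The case against.** **Coverage of CRP is inferred.** The explanatory terms in 9.4.2 are mechanistic endpoints, a term not defined in the text at hand, and CRP is not named there. Section 9.3.2 keeps the groups apart: "Additional inflammatory biomarkers, clinical and mechanistic endpoints (e.g. target engagement) may be reviewed if available". CRP is described under clinical disease assessments, and the Time and Events Table gives it a row separate from the pharmacodynamic inflammatory biomarkers. This stands, so the point is conditional. The inference is still fair. Section 3 lists CRP as a blood inflammatory marker, and 9.1 covers pharmacodynamic as well as mechanistic parameters, so the label does not decide the matter. Target engagement is an exploratory endpoint, so it is unlikely to be all that is meant under secondary analyses.

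**The test is optional and loosely specified.** The model comparison is only one permitted route, no significance level is given, and the study is not powered and tests no formal hypothesis. This also stands: the rejection rates describe an assumed test. But any association model with CRP on one side and DAS28-CRP on the other shares the overlap.

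**Details belong in the Reporting and Analysis Plan.** Model details do, and that plan is not at hand and may already handle the overlap. The protocol itself, however, fixes the claim to be made, the example outcome and the all-parameter scope, and the circular pair follows from those.

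**Stronger readings that the documents do not support.** A reader might infer that ACR is affected as badly as DAS28-CRP; its structure and the simulation show otherwise. A reader might infer that a drug lowering only CRP would seem to produce clinical benefit on every measure; it could not by itself create ACR responders, because both joint counts must improve. The size of the effect for Vectra DA as a predictor was not calculated.

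**Conclusion.** The point holds in conditional form. If CRP is used to explain DAS28-CRP, as the scope in 9.1 implies, the association is partly built in. With 24 subjects a nominal 5% test would call it significant about 18% to 80% of the time, although CRP is unrelated to the rest of the score.

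The size rests on the assumed 5% to 30% variance share and on full independence between CRP and the other components. Independence is an extreme case, chosen to isolate the arithmetic part. If CRP is truly related to joints and patient global, the overlap adds to a real association.

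For ACR the excess is at most about 5 points, so a caveat is enough. The primary safety objective is untouched, and so is the comparison of DAS28-CRP between arms. This is a cheap improvement to a secondary analysis, not a flaw in the design.

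**What to change.** Add to Section 9.4.2, with a cross-reference in 9.1 (or carry it into the Reporting and Analysis Plan):

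> When the explanatory marker is CRP, or a score that contains CRP such as Vectra DA, the clinical outcome is the non-CRP part of DAS28: tender and swollen joint counts and patient global. Associations of these markers with DAS28-CRP are shown descriptively and are not interpreted as explanatory. Where CRP is related to ACR response, the report notes that CRP is one of the ACR components.

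It would also help to state which endpoints count as mechanistic, so that it is clear whether CRP is among them. DAS28-CRP remains the endpoint for the treatment comparison.

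The cost is one derived variable and a weaker reported association for CRP. No new data are needed: the Time and Events Table already collects joint counts, patient global and CRP at every efficacy visit (Day 8 is not one of them).

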#### 9.2.1. Sample Size Assumptions

The study is not powered to detect pre-defined differences. A sufficient number of subjects will be screened so that approximately 24 subjects with moderate to severe RA are randomised into the study on a TID regimen. Prior to protocol amendment 3 being approved in each country, no more than 18 subjects will be randomised into the study on a BID regimen. [Table 4](#) summarises the total planned sample sizes for BID and TID regimens. Should the drop-out rate be higher than anticipated, additional or replacement subjects may be randomised (up to an overall total maximum of 48) into the study at the discretion of the Sponsor.

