**Figure 4 One Event in 16 Subjects: Beta (2,16) Distribution**

Thus, we can be 95% certain that the true probability of the safety event lies between 2% and 25%.

For supportive information, the properties of the key secondary endpoint DAS28 have been considered.

Based on the estimate of variability (SD=1 from historical data) it is estimated that the lower and upper bounds of the 95% CI for the change from baseline in DAS28-CRP score will be within approximately 0.693 and 0.490 of the point estimate of GSK2982772 60 mg TID (n=16) and placebo (n=8).

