### 5.4. Withdrawal/Stopping Criteria

Subjects may be withdrawn from the study for any of the following reasons:

- A subject may withdraw from study treatment at any time at his/her own request, or may be withdrawn at any time at the discretion of the Investigator for safety, behavioural or administrative reasons. If a subject withdraws from the study, he/she may request destruction of any samples taken, and the Investigator must document this in the site study records. The reason for withdrawal should be documented in the Case Report Form (CRF).
- The Sponsor's request, for reasons such as significant protocol deviations (and after discussion with the Investigator).
- If a subject is withdrawn from study treatment, this subject is also considered to be withdrawn from the study.
- Study is terminated by the Sponsor.

If a subject is withdrawn, the Sponsor may decide to replace that subject and this will be done through the Interactive Response Technology System (IRTS).

If a subject chooses to withdraw from the study after dosing then the Investigator must make every effort to complete the follow-up assessments detailed in the Time and Events Table (Section 7.1).

The following actions must be taken in relation to a subject who fails to attend the clinic for a required study visit:

- The site must attempt to contact the subject and re-schedule the missed visit as soon as possible.

- The site must counsel the subject on the importance of maintaining the assigned visit schedule and ascertain whether or not the subject wishes to and/or should continue in the study.
- In cases where the subject is deemed ‘lost to follow up’, the Investigator or designee must make every effort to regain contact with the subject (where possible, 3 telephone calls and if necessary a certified letter to the subject’s last known mailing address or local equivalent methods). These contact attempts should be documented in the subject’s medical record.
- Should the subject continue to be unreachable, only then will he/she be considered to have withdrawn from the study with a primary reason of “Lost to Follow-up”.

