## 6.2. Treatment Assignment

At Screening a unique Subject Number will be assigned to any subject who has signed a consent form. The unique Subject Number will be used to identify individual subjects during the course of the study. Any subject that is re-screened outside of the allowed screening window at the approval of the GSK Medical Monitor, must be assigned a new unique Subject Number .

Subjects who meet screening eligibility criteria will be randomised to a treatment group through an Interactive Response Technology System (IRTS). The IRTS will confirm the subject's CRF number (Subject Number) and provide the randomisation number, where:

- A randomisation number will be assigned from a randomisation schedule generated by Clinical Statistics, prior to the start of the study, using validated internal software. Once assigned, this number must not be reassigned to any other subject in the study.

Therefore, the randomisation is centrally controlled by the IRTS.

Subjects will be randomised to receive either GSK2982772 or placebo in a 2:1 ratio.

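### The per-visit GEE comparison of responder rates, run in its usual logit, robust-SE, Wald form with 16 active and 8 placebo subjects, yields spurious significance when an arm has no responders

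*Protocol*

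**What the plan says.** Protocol Section 9.4.2 makes the treatment comparison of secondary endpoints conditional on its being deemed appropriate. It then brings in the responder endpoints: "Additionally, this could include, the proportion of subjects achieving ACR20/50/70 and DAS28-CRP response". The method attached to them in the same sentence reads: "which will be statistically analysed using a Generalised Estimating Equation (GEE) model comparing GSK2982772 with placebo at each timepoint". The choice left open is whether the comparison is run; if it is run, the method is GEE. No link function, working correlation, variance estimator, test statistic or rule for sparse data is given, and Section 9.4.3 leaves further detail to the Reporting and Analysis Plan (RAP).

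On size, Section 9.2.1 plans that "approximately 24 subjects with moderate to severe RA are randomised into the study on a TID regimen". Allocation is 2:1 (Section 6.2), and the precision calculation in Section 9.2.1 uses "60 mg TID (n=16) and placebo (n=8"). Before Amendment 3, "no more than 18 subjects will be randomised into the study on a BID regimen". Under Section 9.3.1, if 12 or more subjects enter on BID, only the active arm is split by dosing frequency, so placebo subjects from both regimens may be analysed together.

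**The concern.** A logistic model has no finite treatment estimate at a visit where one arm has no responders. With 8 placebo subjects and a strict criterion such as ACR50 or ACR70, such visits can be frequent. The usual robust standard error does not warn of the problem. It stays small while the estimate runs off, so the Wald test reports an extreme p-value from data that carry almost no evidence. Response proportions are listed secondary endpoints, and a p-value below 0.0001 resting on one or two active responders could be read as a clear efficacy signal.

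**Working it through.** **The plan's own figure.** Section 9.2.1 gives DAS28-CRP half-widths of 0.693 and 0.490 with SD 1. The formula 1.96 × SD/√n gives 1.96/√8 = 0.693 and 1.96/√16 = 0.490. Both reproduce and confirm the arm sizes of 8 and 16. (The sentence lists the two half-widths in the reverse order to the arms. The same section also mentions 20 subjects on active TID, which does not fit 24 at 2:1; 16 is used here.)

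**Assumptions, because the protocol is silent.** Two-sided 5% level; the same true response rate in both arms, varied from 5% to 40%; one visit; logit link, robust standard error, Wald test.

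**Example, 2/16 against 0/8.**
- Active log-odds: ln(0.125/0.875) = −1.95. Its robust variance is 1/(16 × 0.125 × 0.875) = 0.571, so SE = 0.76.
- Placebo log-odds: tends to minus infinity. The residuals shrink with the fitted rate, so this arm's robust variance tends to no more than 1/8 = 0.125. Adding it gives √(0.571 + 0.125) = 0.83.
- Fitted result: log-odds ratio 21.6, SE 0.76, p about 1e-179. With SE 0.83, z = 21.6/0.83 = 26, so the conclusion is the same. The size of the estimate only reflects where the iteration stopped.
- Fisher's exact test: p = 0.54.
- For 1/16 against 0/8 the GEE p is about 1e-90 and the Fisher p is 1.00. A bias-reduced robust SE does not help (p about 1e-79).

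**How often an arm is empty.** With q = 1 − rate, the chance that exactly one arm has no responders is q^8 + q^16 − 2q^24. At a 10% rate this is 0.430 + 0.185 − 2 × 0.080 = 0.456.

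**Exact rejection with no effect.** These figures enumerate all pairs of binomial outcomes. If both arms have responders and non-responders, the Wald statistic is the difference in log-odds divided by √[1/(n₁p₁(1−p₁)) + 1/(n₀p₀(1−p₀))]. One empty arm counts as a rejection; two empty arms do not.

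| True rate | 0 of 8 | Exactly one arm empty | Logit, robust, Wald, 16 v 8 | Same, placebo pooled, 16 v 14 | Score test, 16 v 8 | Identity link, 16 v 8 | Fisher, 16 v 8 |
|---|---|---|---|---|---|---|---|
| 5% | 66% | 52% | 52% | 50% | 0.5% | 0.7% | 0.3% |
| 10% | 43% | 46% | 46% | 33% | 3.2% | 3.8% | 0.9% |
| 20% | 17% | 19% | 20% | 8% | 7.9% | 8.7% | 1.6% |
| 30% | 6% | 6% | 8% | 5% | 6.5% | 8.2% | 2.0% |
| 40% | 2% | 2% | 4% | – | – | – | 2.6% |

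At 5% and 10% nearly all rejections come from the empty arm. The pooled figure of 14 is 8 plus 18/3 = 6 placebo subjects from the BID cohort.

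**Six-visit check.** In 300 simulated null trials per setting (assumed latent correlation 0.6, independence working correlation), Day 85 rejection was 51%, 44%, 18% and 8% at rates of 5%, 10%, 20% and 30%, in line with the single-visit figures. With an exchangeable working correlation many fits gave no usable p-value. How many depends strongly on the settings assumed, so no weight is placed on that count.

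**The case against.** The strongest reply is that the failing configuration is not written in the protocol. Section 9.4.2 says only GEE, and other versions behave differently. For 2/16 against 0/8 a score test gives p = 0.16 and an identity-link model p = 0.13. A model-based SE fails in the opposite direction (p = 0.9996). A reader might therefore infer that GEE as such breaks down here; the text does not support that. What stands is that the failing version is the common default and the protocol has nothing to steer the analyst away from it.

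The comparison is also conditional, the study is not powered, and no significance level is set. That lowers the weight of the point. It does not make the named method suitable once the comparison is run.

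A reader might infer that a go/no-go decision hangs on these p-values. Section 9.3.2 names DAS28-CRP as the futility measure and otherwise speaks only of key clinical and mechanistic data. Nothing ties a decision to a responder p-value.

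A reader might also infer that treatment failures drop out of the denominator, since Section 5.4 says "If a subject is withdrawn from study treatment, this subject is also considered to be withdrawn from the study". The protocol does not say how responder status is set after withdrawal. Counting such subjects as non-responders before fitting a GEE is compatible with the text and can be settled in the RAP, so no error is shown there.

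**Conclusion.** The concern holds for sparse responder endpoints analysed with the usual logit, robust-SE, Wald GEE. With 16 against 8, the false-positive rate at one visit is about half at true rates of 5% to 10%, 20% at a rate of 20% and 8% at 30%, and it is no longer inflated at 40%. Pooling placebo to 14 brings it close to nominal at 30% (5%) and to 8% at 20%, but leaves 33% at a 10% rate and 50% at 5%.

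These sizes rest on assumed response rates, an assumed two-sided 5% level and an unstated but common implementation. That ACR50 and ACR70 are the sparse endpoints is likely from their stricter thresholds but is not shown by any rate in the protocol. The results do not justify removing GEE from endpoints where both arms have a fair number of responders. The change should be made before unblinded responder data are analysed; as these are secondary endpoints without formal hypotheses, it does not affect the primary safety objective.

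**What to change.** Amend the sentence in Section 9.4.2 and carry it into the RAP:
- For ACR20/50/70 and DAS28-CRP response, report the per-visit difference in proportions with an exact interval or a Beta(1,1) posterior interval, at least whenever an arm has no or few responders. Define few in advance. The Beta(1,1) prior is already used in Section 9.2.1.
- Do not report Wald p-values from a robust-SE logistic GEE in those cases. GEE may stay for endpoints that are not sparse, with link, variance estimator and test named.

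At 16 against 8 with no effect, rejection is at most about 3% for Fisher's exact test and about 5% for the Beta posterior (probability of superiority above 0.975 or below 0.025).

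The cost is one protocol sentence and RAP wording. The downside is that separate per-visit comparisons do not borrow information across visits.
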